7.22.1.2 Serious Adverse Event

A serious AE (SAE) is any AE occurring at any dose that results in any of the following outcomes:

- Death
- Is life-threatening
- Requires inpatient hospitalization
- Requires prolongation of existing hospitalization
- A persistent or significant disability or incapacity
- A congenital anomaly or birth defect

Important medical events that may not result in death, be life-threatening, or require hospitalization may be considered an SAE when, based upon appropriate medical judgment, they may jeopardize the patient and may require medical or surgical intervention to prevent one of the outcomes listed in this definition. Examples of such medical events include allergic bronchospasm requiring intensive treatment in an emergency room or at home, blood dyscrasias or convulsions that do not result in inpatient hospitalization.

The National Cancer Institute Common Terminology Criteria for Adverse Events (CTCAE) grading scale should be referenced when assessing the severity of an AE (see [Appendix 6](#)). If an AE is not described in the NCI CTC, the severity should be recorded based on the scale provided in [Table 7-3](#).

The severity of all AEs/SAEs should be recorded on the appropriate eCRF page as Grade 1, 2, 3, 4, or 5 corresponding, respectively, to a severity of mild, moderate, severe, life-threatening, or death.

Table 7-3 Adverse Event Severity

Severity	Definition
Grade 1 (Mild)	No limitation of usual activities.
Grade 2 (Moderate)	Some limitation of usual activities.
Grade 3 (Severe)	Inability to carry out usual activities.
Grade 4 (Life-threatening)	Immediate risk of death.
Grade 5 (Death related to an AE)	Death

Relationship of an adverse event or serious adverse event to study medication is to be determined by the Investigator based on the definitions in [Table 7-4](#):

Table 7-4 Adverse Event Relatedness

Relationship to Product(s)	Definition
Not Related	Unrelated to study drug.
Possibly Related	A clinical event or laboratory abnormality with a reasonable time sequence to administration of study drug, but which could also be explained by concurrent disease or other drugs or chemicals.
Probably Related	A clinical event or laboratory abnormality with a reasonable time sequence to administration of study drug, unlikely to be attributable to concurrent disease or other drugs and chemicals and which follows a clinically reasonable response on de-challenge. The association of the clinical event or laboratory abnormality must also have some biologic plausibility, at least on theoretical grounds.
Definitely Related	The event follows a reasonable temporal sequence from administration of the medication, follows a known or suspected response pattern to the medication, is confirmed by improvement upon stopping the medication (dechallenge) and reappears upon repeated exposure (rechallenge). Note that this is not to be construed as requiring re-exposure of the patient to study drug; however, the determination of definitely related can only be used when recurrence of event is observed.

7.22.2 Procedures for Recording and Reporting Adverse Events

7.22.2.1 Reporting Serious Adverse Events Related to Study Procedures

Any SAE that occurs in a patient after informed consent (and assent if applicable) should be recorded by the clinical site on an SAE form that is to be transmitted to the Shire HGT Medical Monitor and to the Shire Pharmacovigilance and Risk Management Department at the contact number provided below. The SAE must be completely described on the patient's eCRF, including the judgment of the Investigator as to the relationship of the SAE to the study procedure. The Investigator will promptly supply all information identified and requested by the Sponsor (and/or contract research organization [CRO]) regarding the SAE as to the relationship of the SAE to study drug, device or procedure.

The SAE form must be completed and FAXED or scanned and EMAILED (PDF sent by e-mail) within 24 hours of the Investigator's learning of the event to:

Shire Pharmacovigilance and Risk Management Department:

International FAX: [REDACTED] **United Kingdom OR**

United States FAX: [REDACTED]

Email: [REDACTED]

AND

Shire HGT Medical Monitor:

FAX: [REDACTED] **(United States)**

The Investigator may also call the Medical Monitor directly (optional):

Shire HGT Medical Monitor: [REDACTED], MD

[REDACTED]

Shire HGT

Work: [REDACTED]

Cell: [REDACTED] **(24 hour access)**

Email: [REDACTED]

AND

Clinical Project Manager CC'd: [REDACTED]

Any follow-up information must also be completed on an SAE form and faxed or scanned to the same numbers or e-mail address listed above.

In the event of a severe and unexpected, fatal, or life-threatening SAE, the clinical site must contact the Shire HGT Medical Monitor by telephone; this is in addition to completing and transmitting the SAE form as stated above. The following provides contact information for the Shire HGT Medical Monitor.

If an SAE is assessed as severe and unexpected, or life-threatening, contact:

[REDACTED] MD
[REDACTED]
Shire Human Genetic Therapies, Inc.
[name]
[name]
Telephone: [REDACTED]
Fax: [REDACTED] (United States)
Mobile: [REDACTED] (24-hour access)
[REDACTED]

The Investigator must promptly report all required information to the Institutional Review Board (IRB)/Independent Ethics Committee (IEC). It is the responsibility of the Sponsor to ensure that each Investigator receives a copy of any CIOMS I/MedWatch report that has been submitted to the appropriate regulatory agencies notifying them of an unexpected related SAE. The Investigator or Sponsor must ensure that the IRB/IEC receives a copy of the report and that a copy is also filed within their study files. In addition, the Sponsor will also notify the Investigators and IRBs/IECs of all deaths that occur during the study, irrespective of relationship to study medication

7.22.2.2 Eliciting Adverse Events

Patients should be asked non-leading questions (eg, “How do you feel?”) and further questions should be posed if there is indication of an AE. The questioning should be conducted with due regard for objectivity and, in particular, the questioner should gather information regarding AEs from questioning the patient, the patient’s parent/guardian, spontaneous report by the patient or parent/guardian, laboratory reports, and any health care provider’s observations.

The onset date, resolution date, treatment administered, and outcome of each AE must be recorded on the appropriate eCRF. In addition, the relationship of each AE to study medication must be recorded.

7.22.2.3 Protocol Deviations for Medical Emergency or Adverse Event

During and following a patient’s participation in the study, the Investigator should ensure that adequate medical care is provided to a patient for any AEs, including clinically significant laboratory test results.

The Investigator should inform the patient, the patient’s parent(s), or the patient’s legally authorized representative when medical care is needed for intercurrent illness(es) of which the Investigator becomes aware. In an emergency situation, the Investigator should contact the Shire HGT Medical Monitor (see Section 7.22.2.1).

Only when an emergency occurs that requires an immediate deviation from the protocol for the safety of a patient, will there be such a deviation and this will be only for that patient.

The Investigator or other physician in attendance in such an emergency must contact the Shire HGT Medical Monitor as soon as possible.

The Investigator, along with the Shire HGT Medical Monitor, will make a decision as to whether or not the patient should continue in the study prior to the next scheduled dose. The departure from the protocol and the grounds for it should be stated in the eCRF.

7.23 Safety-related Study Stopping Rules

If any patient experiences a life-threatening (Grade 4) adverse event or death which is considered possibly, probably, or definitely related to study drug, or if 2 or more patients experience a Grade 3 adverse event during the trial that is considered possibly, probably, or definitely related to the study drug by the sponsor, then the site will be instructed to halt further rhHNS administration to all patients and the safety data reviewed. Following a review of safety data, the study will be either:

- Resumed unchanged
- Resumed with modifications to the protocol or
- Terminated

Patient safety will be monitored on a continuous basis during this study until the last patient completes his or her last scheduled study visit/assessment.

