Patients will be evaluated for safety throughout the study. Adverse events that occur in HGT-SAN-055 and are ongoing at enrollment in HGT-SAN-067 will be captured as ongoing in the HGT-SAN-055 study and also be reported as a concurrent condition in the HGT-SAN-067 electronic case report forms (eCRFs). Specific safety stopping criteria will be applied and will be based on the types and severity of AEs reported while on-study. These data will be reviewed to inform the decision to discontinue a patient, a dose group, or the study as a whole.

All patients will have an EOS visit 30 (\pm 7) days following their last administration of rhHNS (ie, Month 55). The EOS procedures will include standard clinical laboratory tests (serum chemistry, hematology, and urinalysis) in CSF and blood, protocol specific laboratory testing (eg, anti-rhHNS antibody testing), neurodevelopmental testing, ABR, child health questionnaires, and MRI. Use of concomitant medications, therapies, and procedures will be recorded and AEs will be monitored.

All patients will be contacted by telephone or will have a visit for a Final Safety Follow-up, conducted at 30 (\pm 7) days after the EOS visit (ie, Month 56) to collect updated information on AEs and concomitant medications, therapies, and procedures.

It is anticipated that the IDDD will be used to obtain CSF samples and to deliver administrations of rhHNS. However, if a patient's IDDD appears nonfunctional or if its use is precluded on a scheduled day of dosing, site personnel will refer to protocol [Appendix 3](#) which describes the investigation and management of IDDD-related issues. This will include possible partial revision or complete replacement of the IDDD. A maximum of 2 partial revisions and/or complete replacements are permitted in any 6 month period (including participation in study HGT-SAN-055). If a revision or replacement of the IDDD cannot be scheduled in time to avoid a delay of the next scheduled dose of rhHNS, or if the patient experiences more than 2 IDDD malfunctions in a 6 month period, rhHNS will be administered via LP. Drug may be administered via LP for a maximum of 5 successive monthly doses, after which, IDDD re-implantation or revision must occur.

If there is no significant safety risk in the opinion of the Investigator, a non-functional IDDD may be left in situ for up to 3 months.

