3. If IDDD mechanical failure is confined to the port, its attachment to the catheter, or to the segment of catheter immediately adjacent to the port, proximal revision of the IDDD may be undertaken. In such an event, the old port and locking assembly is removed. New components are then implanted, leaving the original catheter in situ. However, the end of the catheter must be trimmed by at least one centimeter to restore a tight connection with the new port outlet tube. The patency of the apparatus must be ascertained intra-operatively, by aspirating CSF through the port, and flushing the device with sterile normal saline.

4. If IDDD mechanical failure is due to dislodgment of the catheter from the spinal canal, kinking at a location distal to the immediate vicinity of the port, or unresolved by proximal revision, the whole device must be replaced, following the instructions provided by Smith's Medical and the Shire training materials.

Note: All removed IDDDs must be returned to Smith's Medical for further analysis. Please refer to the Study Manual for instructions on the IDDD Return process. You should also contact Shire HGT.

Note: All IDDD related AEs (serious and nonserious) will be reported to Shire; all IDDD related SAEs will also be reported to Global Shire PVRM.

Drug Administration Following Device Revision:

1. If a full revision of the IDDD has been performed, an interval of 7 days is required before resuming administration of drug via IDDD.
2. If a proximal (ie, replacement of port only) revision of IDDD has been performed, drug administration through the IDDD can proceed immediately post-operatively.
3. In the event that the IDDD fails after 2 revisions in a 6-month time period, rhHNS may be administered and CSF collected by lumbar puncture for up to 5 successive months after which, IDDD re-implantation or revision must occur.

Appendix 4 Summary of Changes for Amendment 3

Clinical protocol HGT-SAN-067 has been revised from the previous version (Amendment 2, 13-Jan-2012) to update the study drug description to reflect a change in formulation. The protocol was also revised for the following purposes:

- Update the sponsor's contact phone number
- Clarify the timing of the neurological examination on days of study drug administration
- Clarify that Full Developmental Testing includes VABS-II
- Remove duplicative text describing the adverse events due to systemic exposure to rhHNS

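### The mandatory dosing halt in Section 7.23 covers only drug-related events, so a death or life-threatening event due solely to the IDDD or the dosing access leaves any study-wide pause to discretion

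*Protocol*

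**What the plan says.** The current text is Amendment 3. Its automatic rule in Section 7.23 has two triggers. The first is "If any patient experiences a life-threatening (Grade 4) adverse event or death which is considered possibly, probably, or definitely related to study drug". The second is a Grade 3 event in at least two patients, with the same three levels of relatedness to drug as judged by the sponsor. Either one stops rhHNS in all patients and starts a safety review. That review ends in resumption without change, resumption under a modified protocol, or termination. Amendment 2 has the same rule.

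Section 4.1 speaks more generally: "Specific safety stopping criteria will be applied and will be based on the types and severity of AEs reported while on-study". It continues: "These data will be reviewed to inform the decision to discontinue a patient, a dose group, or the study as a whole". It names no threshold, no attribution and no automatic action.

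Device and procedure harm is recognized elsewhere:

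- Section 7.22.1.1 treats IDDD-related events as a class of their own. It lists sepsis, meningitis and spinal cord injury among the risks of the device and of intraspinal access.
- For serious events, Section 7.22.2.1 has the investigator supply information "regarding the SAE as to the relationship of the SAE to study drug, device or procedure".
- Appendix 3 states: "All IDDD related AEs (serious and nonserious) will be reported to Shire; all IDDD related SAEs will also be reported to Global Shire PVRM".
- Section 7.22.2.1 adds that "the Sponsor will also notify the Investigators and IRBs/IECs of all deaths that occur during the study, irrespective of relationship to study medication".
- Section 10.6.1.1 summarizes device-related events separately.

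**The concern.** Section 10.1 states the primary objective as the long-term safety of giving rhHNS through the surgically implanted IDDD, so the route is part of what is being tested. Every scheduled dose needs either port access or a lumbar puncture (Sections 6.2.3 and 6.2.4). If one child died of meningitis traced to the port and judged unrelated to drug, the other children could be exposed to the same access at their next monthly dose. Nothing would require a review before then. For an equally severe drug-related event the sponsor has made the pause automatic. At stake is whether the same certainty should apply to the route, in a trial with no data monitoring committee.

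**Working it through.** The plan gives no figure to reproduce. The check is a reading of the rule, followed by the cost of a pause.

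1. **Apply the rule.** Take a death, or a life-threatening event, rated unrelated to drug and related only to the IDDD or the dosing access. The first trigger fails on attribution. The second fails on attribution too. Both triggers are tied to drug; neither covers device or procedure.

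2. **Look for another mandatory study-wide halt.**
   - Section 4.1: review informs a decision; no action is fixed.
   - Section 7.22.2.3: in an emergency, continuation is decided before the next dose, for the affected patient only.
   - Section 7.25: removal is discretionary and for one patient. The grounds include problematic intubation and refractory spinal fluid leakage.
   - Section 8.2: a dose is withheld if the pre-dose CSF has more than 100 WBC per cubic millimeter, again in one patient.
   - Sections 11.12.1 and 11.12.2: the study or a site may be terminated.
   - Section 11.8: no data monitoring committee.

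   None obliges a pause for the other children.

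3. **Find the edge of the gap.** Table 7-4 sets a low bar for its lowest positive rating: "A clinical event or laboratory abnormality with a reasonable time sequence to administration of study drug, but which could also be explained by concurrent disease". An intrathecal event soon after a dose will often qualify, and it then triggers Section 7.23 as written. Only events attributed solely to device or access remain.

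4. **Ask what a halt removes.** Section 7.23 stops rhHNS administration and nothing else.
   - Removed until review: port access for dosing and pre-dose CSF sampling, lumbar puncture for the same purposes, and the sedation or anesthesia given for them.
   - Not removed: the implant itself; revision or replacement surgery, which Section 7.12 prescribes for a nonfunctional or infected device; and anesthesia for MRI or ABR (Section 7.9).

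5. **Exposure on the route.** Inputs are 4 years (Section 4.3), every 28 days ±7 (Section 6.2.1) and at most 12 patients (Section 5.1).
   - Doses per child: 4 × 365.25 / 28 = 52.2, about 52; counted monthly, 4 × 12 = 48.
   - All children: 12 × 48 = 576 to 12 × 52 = 624 accesses. This is an upper bound that assumes 12 children all complete. It counts accesses, not harm.

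6. **Cost of one pause.**
   - Delay inside the ±7-day window: no dose lost.
   - 28 days: one dose per child, 1/52 = 1.92% to 1/48 = 2.08%; at most 12 doses in all.
   - 56 days: two doses per child, 2/52 = 3.85% to 2/48 = 4.17%; at most 24 doses in all.

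**The case against.** The strongest reply is that this is a design choice and not an error. Section 7.23 supplies the automatic part and Sections 4.1 and 11.12.1 supply the judgment. Nothing shows that judgment would fail after a child's death. Many device failures are mechanical and specific to one implant, so controls for single patients or sites suit them, and Appendix 3 sets out their management. Interrupting treatment also costs something, because the disease is progressive and Section 1.1 says no disease-modifying therapy is approved.

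Much of this stands. It limits the point to a narrow class of events and rules out a broad remedy. It does not make a discretionary pause equivalent to a mandatory one, and the sponsor chose the mandatory form for drug-related events.

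Some stronger readings are tempting, and the documents do not support them:

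- *Device-related deaths go unnoticed.* They do not. SAEs are reported within 24 hours, IDDD-related SAEs also go to pharmacovigilance, and deaths are notified whatever their cause.
- *Section 4.1 contradicts Section 7.23.* It does not. It is more general and promises no automatic action for any attribution.
- *Any event involving the device escapes the halt.* Only one judged unrelated to drug does.
- *Every surgical or anesthetic event should halt dosing.* Stopping rhHNS does not stop revision surgery or MRI and ABR anesthesia, so the pause would cost doses and leave the cause in place.

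**Conclusion.** The point holds in a limited form. A death or life-threatening event attributed solely to the IDDD or to the dosing access triggers no mandatory study-wide pause. Here dosing access means port access, or lumbar puncture for dosing or pre-dose CSF sampling, with its sedation or anesthesia. The response is left to discretion even though safety by this route is the stated primary objective and there is no data monitoring committee. It is a cheap improvement and not a mistake in the plan.

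The benefit is confined to exposures that a dosing halt removes and to changes that a review could order. The protocol gives no rate for such events, so no probability or number of harms avoided can be stated. The cost figures assume the full 4-year schedule. The conclusion rests on Amendments 2 and 3; whether another version changes Section 7.23 could not be checked.

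**What to change.** Extend only the first trigger of Section 7.23. Keep its present drug-related wording and add a death, or an adverse event meeting the life-threatening criterion in Section 7.22.1.2, that is possibly, probably or definitely related to the IDDD in use or to the dosing access procedure, including sedation or anesthesia given for it.

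- **Use the SAE criterion, not the printed Grade 4, for the added part.** CTCAE v3.0 in Appendix 6 puts fever above 40.0°C for more than 24 hours, and apnea with intubation indicated, at Grade 4. Rated only possibly procedure-related, such entries could halt the study too readily.
- **Do not add implantation or revision surgery, or MRI or ABR anesthesia.** A dosing halt does not remove those exposures.
- **Leave the Grade 3 trigger drug-related.** Appendix 6 grades device replacement or removal as Grade 3, so expected revisions would otherwise stop the trial.
- **Keep the existing review and its three outcomes.**

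No new data collection is needed. Section 7.22.1.2 says "A serious AE (SAE) is any AE occurring at any dose that results in any of the following outcomes", and both death and life-threatening events are on that list. Section 7.22.2.1 already covers relatedness to device and procedure for them.

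The textual change is one sentence. The practical cost is an occasional temporary interruption of monthly dosing in a progressive disease: about one dose, roughly 2%, per child per 28 days of pause. Prompt review and the option to resume without change limit it.

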7.24 Pregnancy

Pregnancy and breast feeding are exclusion criteria. Only female patients who have reached menarche will be tested for pregnancy in HGT-SAN-067. If applicable, this will occur at study start and before each dose of rhHNS throughout the study. Pregnancy testing will be performed on a blood or urine sample. Patients with a positive or inconclusive result will not be eligible for this study.

At study start, a pregnancy test will be performed if more than 30 days have passed since the initial screening sample. Throughout the study pregnancy testing will occur prior to each dose of rhHNS. The clinical site's local laboratory will analyze and report all pregnancy testing results. If a pregnancy test is positive the patient will be discontinued from the study, and the Investigator must contact the Shire HGT Medical Monitor.

Pregnancy is not to be reported as an AE; the Pregnancy Reporting Form, found in the Study Operations Manual along with instructions for completion, should be used to report the pregnancy. The pregnancy will be followed up through delivery or final outcome.

7.25 Removal of Subjects from the Trial or Study Drug

The patient's parent or legally authorized representative acting on behalf of the patient is free to withdraw consent and discontinue participation in the study at any time without prejudice to further treatment. Since this is an extension trial, there will be no replacement of patients who discontinue the study for any reason.

A patient's participation in the study may be discontinued at any time at the discretion of the Investigator, Sponsor, or Medical Monitor. The following may be justifiable reasons for the Investigator, Sponsor, or Medical Monitor to remove a patient from the study:

- Adverse Event: If a patient experiences an AE which, in the judgment of the investigator, the sponsor, or the medical monitor, presents an unacceptable consequence or risk to the patient.
- Adverse Laboratory Experience: If a patient has an adverse laboratory experience which, in the judgment of the investigator, the Sponsor, or the medical monitor, presents an unacceptable consequence or risk to the patient, the patient may be withdrawn from the study.
- Comorbidity: If a patient develops comorbidity during the course of the study that is independent of the study indication, and treatment is required that is not consistent with protocol requirements.
- Intercurrent Illness: If a patient develops an illness during the course of the study that is not associated with the condition under study, and which requires treatment that is not consistent with protocol requirements.
- Refusal of Treatment: If the patient, the patient's parent(s) or legally authorized representative(s) discontinues participation in the study, or the patient is discontinued by the Investigator, reasonable efforts will be made to follow the patient through the end of study assessments. The reason for refusal will be documented on the eCRF.
- Withdrawal of Informed Consent: A patient's parent or legally authorized representative may withdraw his informed consent to participate in the study at any time.
- Cerebrospinal fluid leukocyte count >100 cells per cubic millimeter for 2 consecutive months.
- New onset seizure.
- Anaphylactic reaction beyond reasonable management as described in the Investigator's Brochure.
- Clinically problematic intubations or extubations, which may preclude safe airway management and anesthesia.
- Development of refractory spinal fluid leakage.
- Clinically significant prolonged (eg, greater than 24 to 48 hours) worsening in mental status, including development of new focal or non-focal neurological symptoms, or recurrence of a previously stable prior medical problem judged due to study drug or participation that is exclusive of effects from anesthesia.
- Non-compliance, including failure to appear at 1 or more study visits.
- The patient was erroneously included in the study.
- The patient develops an exclusion criterion.
- The study is terminated by the Sponsor.
- The patient becomes pregnant during the trial.

If a patient discontinues the study the Patient Completion/Discontinuation eCRF describing the reason for discontinuation must be completed. Any AE's experienced up to the point of discontinuation must be documented on the AE eCRF.

If AEs are present when the patient withdraws from the study, the patient will be re-evaluated within 30 days of withdrawal. All ongoing SAEs at the time of withdrawal will be followed until resolution.

At the time of discontinuation or withdrawal, patients will be asked to participate in all safety and efficacy evaluations required for the end of study visit and for the safety follow-up visit. Participation in these EOS procedures will be strongly encouraged, but is voluntary for those patients electing to discontinue from the study. The patient will be scheduled for the removal of the IDDD.

